1.3 Objectives of the clinical investigation

The proposed clinical investigation is a feasibility study directed toward:

Specific Aim 1: Investigate the safety and efficacy of using NeuroPort Arrays for chronic recording of neural activity from the motor cortex of individuals with upper limb impairments.

- Specific Aim 1a: Document the safety of using the NeuroPort Arrays for chronic recording of neural activity. Monthly neurological and physical examinations will be conducted and documented for the duration of the trial. Any serious adverse events that occur as part of this investigation will be reported in accordance with the FDA’s expedited reporting requirements.
- Specific Aim 1b: Characterize signal quality recorded with the NeuroPort Array during long term implantation in the motor cortex of individuals with tetraplegia. Primary measurements of signal quality include the number of units recorded by the array and the firing rate of single neurons measured during specific tasks (such as imagined hand movement) [6, 45, 46].

Specific Aim 2: Demonstrate that individuals with tetraplegia can learn to successfully control a variety of external devices and computer-driven tasks using signals recorded with two NeuroPort Arrays. We aim to achieve high-dimensional control of complex systems including both a virtual and robotic dexterous hand and arm to perform grasping and reaching tasks which are essential for activities of daily living. This will be measured over the duration of implantation by computing success rate for a given task as well as the amount of computer assist that is required.

Specific Aim 3: Use MEG to localize areas of the brain that can be voluntarily modulated. These results will be compared to pre-surgical mapping results with fMRI and provide additional information for planning the location of electrode implantation.

- Specific Aim 3a: At the optional follow-up MEG visits, we will use the same paradigms to localize areas of the cortex that can be voluntarily modulated to determine if BMI training has induced neuroplasticity. We expect the areas of cortex responsible for voluntary movement will be more strongly activated with more localized responses.

Specific Aim 4: Conduct a sleep study to measure the quantity and quality of sleep each night for a specified period of time to help clarify the role of sleep in motor learning.

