3.4.2 Experimental procedures

This study is an optional extension to PRO10080021. Consent and screening for this study may occur as early as 6 months after implant and up to 13 months after implant (the maximum duration allowed in the original protocol). BMI testing will occur as described in the original protocol with similar ongoing clinical monitoring and follow-up as described below:

Brain-Machine Interface (BMI) Training/Testing:

Neural recording will be conducted for the duration of implantation. The recorded neural data will be used to operate a BMI system that allows the participant to control a computer cursor, virtual object, or assistive device. While the NeuroPort Arrays are implanted, we will conduct BMI training for up to 8 hours per day for up to 5 days per week. At least 1 session per week will be attempted while the array is implanted. BMI testing may occur at the University of Pittsburgh, UPMC, or in the participant's home. Rest, meals, and other breaks will be scheduled as needed. We may not conduct training sessions every day. This will be determined by the research staff and the subject. Also, we may not conduct testing sessions for up to 8 weeks per year. Since participants will have already completed 1 year of testing, we hope to minimize the burden on participants while still collecting valuable data related to signal quality and BMI control. The subject will go no longer than 3 weeks between testing sessions. This will assure that the study team can continue to monitor the wound site and well being of the participant.

At the beginning of each BMI testing session, an investigator will connect the Patient Cable to the Patient Pedestal. We may also record neural activity using EEG electrodes which are placed on the scalp in order to measure larger networks of brain activation. There are two types of behavioral tasks that the subject will participate in as part of the BMI training/testing: 1. Open-loop and 2. Closed Loop. These tasks are the same as described in Section 2.4.2.

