Neural and behavioral data will be recorded during each BMI session in order to address the Specific Aims. As described in Section 2.4.2, we will track neural data, including the number of single units and the average firing rate over the duration of the implant. Behavioral data may include kinematics of a cursor, virtual object, robotic arm, etc. We will also compute the success rate achieved by the participant for a given task over a number of sessions. Impedance measurements will be collected during BMI testing sessions throughout the study. We will also document volunteered or observed adverse events at least weekly as part of the BMI training sessions as a measure of device safety. Subject may be asked at test sessions about level of fatigue, quality of sleep at home or other factors that may affect quality of testing performance.

At the end of each session, an investigator will remove the Patient Cable and clean the device. At a minimum, the Patient Pedestal should be cleaned every 7 days by a family member, caregiver, medical professional, or study team member. We will provide detailed cleaning instructions to the participant and anyone who may assist with the cleaning. We will monitor the subject's temperature on days that BMI testing occurs as this can be an early indicator of infection. In addition, we will instruct the subject to monitor and record their own temperature daily as well. A family member or caregiver will be asked to inspect the Patient Pedestal sites on a daily basis to identify any changes that may indicate an infection such as erythema, drainage, ecchymosis, pain, or unusual redness along the lead tunnel or pedestal. The study neurosurgeon and PI will train the research team and family member or caregiver in how to monitor wound healing.

Sleep Diary:

We may ask the participant to maintain a sleep diary which measures the amount and quality of sleep each night.

In-Home Sleep Evaluation:

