An in-home sleep evaluation may be performed to evaluate how sleep, or lack of sleep, impacts a participant's performance with the neuroprosthetic device. We may measure the participant's brain activity during sleep (in their home) using EEG and/or intracortical recordings from the NeuroPort electrodes. This testing may be completed by a study team member in the subject's home, or in the case of EEG monitoring, it could be conducted by the subject and a caregiver once the electrodes are setup by a study team member. In addition to brain activity, we may record additional physiological information including electrocardiogram (EKG) activity, temperature (using a small sensor near the nose), and respiration (using elastic belts around the chest and abdomen). We will plan to set up the equipment early enough so as not to interfere with their normal sleep routine. The equipment will be removed after their normal wake-up time. We may ask the subject to perform simple BMI tasks before and after periods of normal sleep. Our goal is to determine how normal sleep (including normally occurring variations in sleep quantity and quality) affects neural activity and BMI performance.

Ongoing Clinical Evaluations:

A clinical investigator will perform a monthly clinical evaluation to monitor the participant's neurological and musculoskeletal status. Wound checks will also be performed at this visit. If any changes in neurological status or musculoskeletal functioning are noted, appropriate medical care will be provided. These clinical visits will likely be combined with research visits to the University of Pittsburgh or UPMC.

Ongoing Psychological Evaluations:

The subject will have opportunities to talk to a psychologist throughout the study, either over the phone or in person. These discussions will be scheduled regularly (approximately every 3 months) to discuss any concerns the subject may have. The psychologist may refer the subject for additional meetings as necessary. In addition, physician-investigators, including the study PI and neurosurgeon, will be interacting with the subject on a regular basis and can refer the subject to a psychologist at their discretion. If the subject has severe problems or concerns, he or she may be withdrawn from the study.

Imaging:

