Specific Aim 3: Source localization (combining the MEG and structural MRI data) will be used to identify the anatomical foci of cortical activation controlling imagined and/or attempted movement. The coordinates (x,y,z) of the center of activation can be computed with fMRI or MEG relative to the head coordinate system defined using bony landmarks. The location and area of cortical activation measured by fMRI and MEG during imagined and/or attempted movement will be compared for each subject. A paired t-test will be used to compare location and area of cortical activation measured by the two imaging techniques using data from all participants, although the power of this test may be limited by sample size. Qualitative comparisons will be informative and we expect agreement between the two imaging techniques in terms of localizing the area for array implantation. MEG potentially offers additional information due to higher temporal resolution.

Specific Aim 3a: Cortical modulation will be calculated as the power of the 4-40 Hz frequency band of MEG data that is recorded during imagined and/or attempted movement. Specific Aim 3a will be evaluated by applying repeated measures ANOVA to test for differences in modulation (magnitude and total area) during imagined and/or attempted movement during the pre-surgical procedures and the follow-up sessions.

Specific Aim 4: Sleep quality measures will be correlated to BMI performance on the following day while controlling for differences in task difficulty. Linear regression will be used to determine the most predictive sleep quality metrics.

The study will be considered a success if the device is not explanted for safety reasons during the 12-month to 5 year post-implant evaluation. This study is not being proposed to support marketing applications (510(k) or PMA) for the NeuroPort Arrays. Instead, the goal is to demonstrate that three-dimensional microelectrode arrays provide a safe way to record sufficient neural information for controlling complex assistive devices that will increase the independence of individuals with disabilities.

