Individuals may experience frustration during BMI training sessions, particularly early in the study. For the extension study, participants will be informed that it is likely that signal quality will degrade over time. This may make it more difficult to complete the tasks so the difficulty and complexity may need to be reduced. Participants can be scheduled for appointments to speak with a psychologist throughout the study (approximately 1, 3, 6 and 9 months after implantation and again prior to explantation) to discuss any concerns they have during the study. The visits will occur every 3 months during the extension study as well. In addition, physician-investigators may refer the subjects to additional psychological appointments at their discretion.

Risks of EEG/EKG Recording (Extension Study)

Minor skin irritation may develop from the placement and removal of EKG and EEG electrodes.

Steps taken to minimize these risks:

Cleaning the skin after removal of the electrodes will reduce the risk of skin irritation. If skin irritation does occur, an over-the-counter ointment can remedy this.

Risks of In-Home Sleep Evaluation (Extension Study)

Participant may experience fatigue following sleep evaluation, if amount of sleep was insufficient or below normal amount.

Steps taken to minimize these risks:

Participant and caregiver will be asked to ensure that participant does not perform any activities that would invite risk of injury until the fatigue has subsided..

Risks of Pregnancy (Core Study and Extension Study)

Women who are, or plan to become, pregnant are excluded from the study due to potential risks to the unborn fetus or themselves. These risks include radiation exposure during x-ray or CT imaging which may lead to birth defects, mental impairment, cancer, or miscarriage. There are no known risks associated with undergoing an MRI scan while pregnant and the risks of MRI to the fetus are felt to be very small, but are nevertheless also not known. Any complications during surgery would put the fetus at risk for distress. We do not believe that pregnancy would carry any additional risks while the array is implanted, however this has not been studied and therefore the risks are unknown.

Steps taken to minimize these risks:

Study investigators will discuss the risks of pregnancy during the course of the study and will advise women against becoming pregnant. Women will be advised to notify the study team immediately if they learn they are pregnant.

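### Aim 4 asks about sleep and motor learning, but its only analysis uses next-day performance level and cannot separate learning from alertness

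*Combined protocol and SAP*

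**What the plan says.** Section 1.3 gives the purpose of the Aim 4 sleep study as "to help clarify the role of sleep in motor learning". It lists this aim for the whole investigation and says that the aims carry over unchanged to the extension.

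The analysis appears once, in the extension part (section 3.5.3): "Sleep quality measures will be correlated to BMI performance on the following day while controlling for differences in task difficulty". The next sentence adds: "Linear regression will be used to determine the most predictive sleep quality metrics". The core analysis (section 2.5.3) has no Aim 4 entry. The core procedures (section 2.4.2) and Table 1 contain no sleep measurement.

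Sleep is measured only under section 3.4.2, and every element is optional:

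- Diary: "We may ask the participant to maintain a sleep diary which measures the amount and quality of sleep each night".
- In-home evaluation, which may use EEG or intracortical recording. Its risk entry in section 4.1 is labelled as belonging to the extension.
- Tasks around sleep: "We may ask the subject to perform simple BMI tasks before and after periods of normal sleep".
- A question at test sessions about fatigue, sleep at home and other influences on performance.

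The in-home evaluation has its own stated goal: to find how normal sleep, with its natural variation, "affects neural activity and BMI performance". That goal does not mention learning.

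**The concern.** Learning is a gain that builds up and is kept. The planned outcome is how well the participant performs on the day after a given night. A good night can raise that score because something was consolidated overnight, or because the participant is less tired. The plan adjusts for task difficulty, which bears on neither explanation.

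Timing adds a second limitation. Extension entry (section 3.3.3) requires at least 6 months of implantation and demonstrated control in at least four dimensions. Acquisition of that initial skill is over before any sleep is recorded.

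At stake is the reading of Aim 4. A positive result could be reported as evidence on learning when it shows only an effect of being rested. A null result would say little about learning.

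**Working it through.** The plan states no alpha, power, effect size or number of nights for Aim 4, so there is no figure to reproduce. The check is in three steps. All numerical inputs below are assumptions, and two-sided 0.05 is assumed throughout.

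**1. Aim against analysis.**

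| Needed to speak about learning | In the Aim 4 analysis (3.5.3)? | Elsewhere in the plan? |
|---|---|---|
| Overnight gain, learning rate or retention | No | Optional tasks before and after sleep (3.4.2) |
| Fatigue or alertness | No | Optional question at sessions (3.4.2) |
| Earlier performance level | No | Performance is recorded at every session (3.4.2) |
| Time since implant | No | Known for every session; 1.3 says performance may decline |
| Task difficulty | Yes | Not applicable |

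**2. Why a level cannot separate the two.** For one participant, write next-day level = ability + a·z + c·z + noise. Here z is standardised sleep, a is the alertness effect and c is the overnight learning effect. With assumed ability SD 0.5 and noise SD 0.8,

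correlation = (a + c) / √((a + c)² + 0.25 + 0.64).

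Only the sum a + c enters. Alertness alone (a = 0.4, c = 0) gives 0.4/√1.05 = 0.39. Learning alone (a = 0, c = 0.4) gives the same 0.39.

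For 30 nights, Fisher's z is atanh(0.39) = 0.412, and 0.412 × √27 = 2.14. The chance of significance is about Φ(2.14 − 1.96) = 57%. Simulation with 4,000 runs gives about 59% in both cases. Alertness effects of 0.2 and 0.6 give about 20% and 88%.

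**3. The planned regression, with task difficulty included.** In a second simulation (residual SD 1, sleep SD 1, 4,000 runs per setting), the true learning effect was zero. The share of runs with a significant sleep coefficient was:

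| Alertness effect (SD per SD of sleep) | 15 nights | 31 nights | 61 nights |
|---|---|---|---|
| 0 | 5% | 5% | 5% |
| 0.3 | 17% | 34% | 61% |
| 0.5 | 37% | 73% | 95% |
| 0.8 | 71% | 98% | 100% |

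Adjusting for difficulty does not remove the association.

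The same simulation also set alertness to zero and let a true learning effect of 0.3 or 0.5 accumulate from night to night. The planned model then detected it in only 7% to 16% of runs, because each day's level reflects all earlier nights as well as the last one.

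Two other outcomes were tried with no learning effect:

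- Morning minus evening still carries alertness. At 31 nights it was significant in 18.8%, 43.9% and 82.0% of runs for alertness effects of 0.3, 0.5 and 0.8.
- Change from one evening to the next, which counts only what outlasts the day, stayed at 4.6% to 5.4%. At the 31-night setting it detected a true learning effect of 0.5 in about 44% of runs.

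**The case against.** The strongest reply is that the plan already asks the narrower question. The goal in section 3.4.2 concerns neural activity and performance, the analysis in 3.5.3 matches it, and section 1.3 claims only to help clarify. No passage says that a correlation will be reported as proof of consolidation, so a reader who infers that goes beyond the text. This stands, and it makes the repair easy. It does not remove the mismatch, because the aim still names motor learning.

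A reader might also infer that little learning remains by the extension, given the phrase "Since participants will have already completed 1 year of testing". The documents do not support that:

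- The phrase explains why breaks in testing are acceptable.
- Consent can come from 6 months after implant, and participation starts at consent.
- Section 1.3 plans to study neuroplasticity and novel training methods in this period, and says only that performance may decline.
- Section 3.5.3 keeps degrees of freedom achieved as an outcome.

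Early acquisition is missed, but later learning is not excluded.

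Nor should section 4.1 be cited for fatigue as an influence on test performance. Its sleep-evaluation entry treats fatigue as a possible consequence of a poor night under evaluation. Section 3.4.2 is the passage that links fatigue to testing, and it offers an optional route to measuring it.

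Finally, the simulated rates follow from assumed inputs, and the aim is exploratory, in up to 5 participants. Both points are correct.

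**Conclusion.** The mismatch is real and rests on the text alone: the aim concerns learning, and the analysis concerns next-day level adjusted only for task difficulty. As written, the analysis can support a statement about sleep and next-day performance but not one about sleep and learning.

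The calculations show direction only. The conclusion that alertness and learning are indistinguishable does not depend on the chosen values, because only their sum enters the correlation. The percentages do depend on them.

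The consequence is confined to the interpretation of Aim 4. Safety and the extension's success criterion are unaffected.

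**What to change.** **Wording.** In sections 1.3 and 3.5.3, restate Aim 4 and its conclusion as the association of normal sleep with next-day BMI performance, in line with the goal in section 3.4.2. State that this analysis does not isolate learning.

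**Model.** In 3.5.3, add the previous session's performance on the same task, time since implant and the session fatigue rating as covariates. Report results with and without fatigue, since fatigue probably lies on the path from sleep to performance. A self-rating is imperfect, so adjusting for it reduces the ambiguity but does not remove it.

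**Exploratory learning measures.** Where tasks before and after sleep are run, report overnight change and retention at a later session. Note that plain morning-minus-evening change still carries alertness.

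A fuller redesign would compare overnight change on a new task with that on a practised task. It is a trade-off, and I would not require it:

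- It needs a fresh task for each night and staff in the home evening and morning.
- In the 30-night simulation it held about 5% false positives only when alertness affected both tasks equally. The rate was about 10% with effects of 0.4 (new) and 0.2 (practised), and about 25% with 0.4 and 0.
- It detected a learning effect of 0.4 in only about 26% of runs.

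**Cost.** A narrower stated aim, slightly more analysis, and asking the fatigue question routinely instead of optionally. No extra visits are needed.

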3.5.4 Data and Safety Monitoring Committee

The independent Data and Safety Monitoring Board (DSMB) that oversees the core study, will also oversee the extension study following the procedures described in section 2.5.4. Similarly, the core members of the research team will meet at least monthly to provide additional internal study monitoring as for the core study. We will comply with the IRB's policy for the reporting of serious and unexpected adverse events as described in Chapter 3.0 of the University of Pittsburgh's IRB Reference Manual. Similarly, we will report adverse device events to the FDA in accordance with the agency's expedited reporting requirements.

4.0 Risk Analysis

For each risk, we have noted whether it is applicable to the core study, extension study, or both.

4.1 Anticipated risks

This study involves potentially serious risks. The risks of all experimental procedures are described below along with the steps that will be taken to minimize those risks.

Risks Common to all Study-Related Activities (Core Study and Extension Study)

There is a risk of breach of confidentiality since personal information will be obtained.

Some of the research activities may require the participant to transfer out of their wheelchair such as the MRI, CT, MEG, and x-ray. There is a risk of falling during the transfer.

There is also a risk of pressure sores with any prolonged sedentary activity for individuals with compromised nervous systems, such as those with SCI. This risk is not unique to participating in this study, and it is a common risk for prolonged sitting (e.g. in wheelchairs). This includes imaging sessions (MRI, CT, MEG, and x-ray) as well as BMI training/testing.

Some of the research procedures involve radiation exposure including the pre-operative

chest x-ray, and post-operative head CT and x-ray. The exposure for each procedure is specified below, but the expected total radiation exposure to the head is expected to be 2.6-5.6 rems. More imaging studies may be necessitated by the participant's medical condition. For reference, an annual radiation exposure of 20 rems is permitted to the most sensitive organs of radiation workers by federal regulations. There is no minimal level of radiation exposure that is recognized as being totally free of the risk of causing genetic mutations (abnormal cells) or cancer.

Steps taken to minimize these risks:

Identifiable data will be filed in locked areas immediately after collection. Study ID numbers will be used instead of the participant's name when recording study-related data. The information collected in this study, such as neural recordings, will generally consist of numbers with little or no meaning to the casual observer. Electronic data is stored on password-protected network drives. Staff has been trained regarding the critical nature of participants' privacy, and about the procedures for respecting their privacy and maintaining confidentiality.

The research staff will be trained to assist participants with transfers as well as to perform dependent transfers. If the participant can transfer independently, they will be spotted. Assistive devices (e.g. sliding board or hoyer lift) will be available as necessary.

We will exclude individuals with a recent history of pressure sores from this study. The risk of developing a pressure sore is infrequent and can be significantly reduced by frequent change of sitting position, pressure relief movement, and usage of cushion. The duration of the imaging sessions that require the participants to remain still will be minimized. We will encourage participants to follow their normal pressure relief routines during experimental sessions.

The imaging studies are required to ensure the participant's safety both pre-operatively and post-operatively. The risk associated with the amount of radiation exposure that the subject will receive from this additional x-ray exam is considered to be low and comparable to everyday risks.

Risks of the Screening Interview Neuropsychological Examination, and Post-Operative Visit with Rehabilitation Psychologist (Core Study)

There is a risk of breach of confidentiality as personal information will be recorded.

Steps taken to minimize this risk:

A screening script will be used to determine whether the subject meets the inclusion/exclusion criteria. This information will be recorded using a coded subject ID. If it is determined that the subject is not eligible or does not wish to participate, this information will be destroyed.

Information from the neuropsychological examination will be recorded using a coded

subject ID. If it is determined that the subject is not eligible or does not wish to participate, this information will be destroyed.

Risks of fMRI (Core Study)

MRI is widely used in clinical practice, and the risks of MRI are believed to be very low. There is no ionizing radiation exposure involved and the studies are non-invasive. The magnet will make intermittent, loud, knocking noises that could cause ear discomfort in some people. Also, the rapidly switched magnetic fields used during imaging may cause nerve stimulation (e.g., an uncontrolled twitch or tickle near the waist). It is possible that the subject may experience feelings of anxiety or claustrophobia during the MRI scans. There is also a risk of the MRI scanner attracting metal objects.

Steps taken to minimize these risks:

Steps will be taken to minimize potential discomforts due to noise in the fMRI, such as wearing earplugs and informing the subject about the procedures. Two-way communication will be maintained at all times in case the subject experiences feelings of anxiety or claustrophobia.

The fMRI scanner may attract metal objects. Metallic implants, pacemakers, and other metallic substances are considered contraindications for MRI and therefore would exclude someone from participating in this study. It is possible to use a MRI-compatible ventilator for someone who is normally ventilator-dependent. Therefore this would not exclude someone from participating in this study. The Magnetic Resonance Research Center will also perform their standard screening procedures prior to the scan to ensure the subject's safety.

Risks of Blood Draw for Pre-Operative Screening (Core Study and Extension Study)

The insertion of the needle to draw blood may cause temporary discomfort, bruising from where the needle enters the vein, or soreness. These risks related to the blood draw are anticipated to be common, or expected to occur in 10% or greater of the participants (10 or more out of 100 people).

There is a slight risk of infection. Fainting may occur, but this risk is expected to be rare, or occur in less than 1% of people, or less than 1 out of 100 people.

Steps taken to minimize these risks:

Pre-operative screening will be performed at the Anesthesia Pre-Op clinic which routinely performs this evaluation for neurosurgical candidates. This screening is necessary to ensure that the participants are not at increased risk for complications during surgical procedures.

Risks of Chest X-ray for Pre-Operative Screening (Core Study and Extension Study)

The maximum amount of radiation exposure that participants will receive from the x-ray

exam is approximately 0.3 rem (a unit of radiation exposure) to the area of the body evaluated with minimal exposure of other areas of your body. For comparison, this is a small fraction (1-2%) of the annual radiation exposure (20 rems) permitted to the most sensitive organs of radiation workers by federal regulations. There is no minimal level of radiation exposure that is recognized as being totally free of the risk of causing genetic mutations (abnormal cells) or cancer. However, the risk associated with the amount of radiation exposure that the subject will receive from this additional x-ray exam is considered to be low and comparable to everyday risks.

Steps taken to minimize these risks:

Pre-operative screening will be performed at the Anesthesia Pre-Op clinic which routinely performs this evaluation for neurosurgical candidates. This helps assure minimal radiation exposure and good technique for acquiring the film. This screening is necessary to ensure that the participants are not at increased risk for complications during surgical procedures.

Risks of EKG for pre-operative screening (Core Study and Extension Study)

There is a risk of skin irritation after removal of the electrodes used for EKG monitoring.

Steps taken to minimize these risks:

Pre-operative screening will be performed at the Anesthesia Pre-Op clinic by personnel who are trained to perform EKG screening. Cleaning the skin after removal of the electrodes will reduce the risk of skin irritation.

Risks of Structural MRI with IV Contrast (Core Study)

MRI is widely used in clinical practice, and the risks of MRI are believed to be very low. There is no ionizing radiation exposure involved and the studies are non-invasive. The magnet will make intermittent, loud, knocking noises that could cause ear discomfort in some people. Also, the rapidly switched magnetic fields used during imaging may cause nerve stimulation (e.g., an uncontrolled twitch or tickle near the waist). It is possible that the subject may experience feelings of anxiety or claustrophobia during the MRI scans. There is also a risk of the MRI scanner attracting metal objects. The contrast agent is FDA-approved and used routinely for MRI exams. It contains a material called gadolinium. The injection of contrast may cause discomfort, tingling or warmth in the lips, metallic taste in the mouth, tingling in the arm, nausea, or headache. These symptoms occur in less than 1% (less than 1 in 100) of people and go away quickly. There is a small risk of an allergic reaction to gadolinium; however, a severe allergic reaction occurs in less than one in 300,000 people. Insertion of the needle (small plastic tube) to inject the gadolinium may cause minor pain, bruising and/or infection at the injection site. People with severe kidney failure who receive gadolinium are at risk of developing Nephrogenic Systemic Fibrosis/Nephrogenic Fibrosing Dermopathy (NSF/NFD). This disease causes fibrosis, which is the formation of too much connective tissue in the skin and internal organs throughout the body. People develop skin thickening that may prevent bending and extending joints, resulting in decreased

movement of the joints. The skin changes can cause feelings of burning, itching and pain that can be severe. In addition, people may experience fibrosis that spreads to other parts of the body such as the diaphragm, muscles in the thigh and lower abdomen, and the lining of blood vessels in the lung. NSF/NFD is a serious progressive disease and can result in death. If the subject has severe kidney failure and receives gadolinium, the risk of developing NSF/NFD is 1-5 % (up to 1 to 5 per 100 people). We may require a blood sample (about 1 tablespoon) to check kidney function before gadolinium contrast is injected.

Steps taken to minimize these risks:

Steps will be taken to minimize potential discomforts due to noise, such as wearing earplugs and informing the subject about the procedures. Two-way communication will be maintained at all times in case the subject experiences feelings of anxiety or claustrophobia.

The MRI scanner may attract metal objects. Metallic implants, pacemakers, and other metallic substances are considered contraindications for MRI and therefore would exclude someone from participating in this study. It is possible to use a MRI-compatible ventilator for someone who is normally ventilator-dependent. Therefore this would not exclude someone from participating in this study. The Magnetic Resonance Research Center will also perform their standard screening procedures prior to the scan to ensure the subject's safety.

Participants will be asked to notify a doctor, nurse or technologist if they are allergic to gadolinium, if they have any kidney problems, or if they experience any of these or other side effects. Individuals with renal failure or dysfunction will be excluded from study participation. A physician will be available during the procedure to administer any necessary care if side effects do occur, and to determine when or if the injection of the gadolinium should be stopped.

Risks of MEG Testing (Core Study and Extension Study)

MEG testing has minimal risks. The MEG system records brain activity non-invasively. It does not require implantation of electrodes in the brain or the application of electrodes to the scalp. MEG recording will be conducted with an FDA-approved MEG system (Neuromag®) located in the MEG Center at University of Pittsburgh Medical Center (UPMC). This facility is also used routinely for clinical diagnostics, and the MEG system is well-maintained to be used safely on humans. During experiments, participants will sit in a chair that is part of the MEG system with a comfortable posture. Participants will be asked to keep still during MEG recording and they may become fatigued during the session since long periods of concentration may be required. It is also possible that the subject may experience feelings of anxiety or claustrophobia during MEG testing.

Steps taken to minimize these risks:

We will have a seat belt available to help with postural support and will have the option to conduct the MEG while the participant is in a supine position if necessary. Rest breaks will be incorporated throughout the testing session to minimize the risk of fatigue. We will encourage participants to perform frequent pressure relief movements and will provide a MEG-compatible cushion to reduce the risk of pressure sores. Two-way communication will be maintained at all times in case the subject experiences feelings of anxiety or claustrophobia.

Risks of Surgical Procedures (Core Study Implantation and Explantation and Extension Study Explantation Only)

In general, the surgical risks associated with implanting the NeuroPort Arrays are anticipated to be typical for any surgery for implanting a device in the brain. The risks should be similar to those for implanting a Deep Brain Stimulator (DBS). However, unlike a DBS implant, the NeuroPort Arrays are not implanted deep into the brain, but rather on the surface of the cortex. The risks associated with surgery include adverse reactions to surgical procedure, bleeding during surgery, infection post-surgery and potential tissue damage to the primary motor cortex during implantation of the NeuroPort Arrays. The risks associated with explantation surgery of the NeuroPort Array are similar to those during implantation surgery. Animal study data show that post-explantation, the primary motor cortex heals with no external signs of irreversible adverse effects. There is also a risk of developing a pressure sore during surgery for individuals with SCI.

There is a risk of bone resorption after the two surgeries where the bone flap is removed and replaced. The bone flap may breakdown and not heal properly however this risk is rare (<1%). If this occurs, the study neurosurgeon may perform an additional surgical procedure to replace the bone flap with an artificial material.

The subject will be under general anesthesia for the duration of the surgery. Minor risks of general anesthesia include nausea and vomiting (25%), sore throat (10-50%), post-operative pain (10-30%), headache (20%), drowsiness (50%), dizziness (20%), damage to the teeth or oral tissue (<1%), and peripheral nerve injuries (<0.3%). These risks are common but are typically temporary. Serious risks of general anesthesia, which are very rare (40), include: vision loss or blurriness (0.0008%), hearing loss (0.01%), anaphylaxis (allergic reaction, 0.01%), post-operative cognitive dysfunction (difficulty with concentration and memory, 1% for individuals over the age of 60), respiratory complications (0.03%), cerebrovascular accident (stroke, 1%), and cardiac arrest (<0.01%).

